	Drug type and cumulative sedative dose	**	**	**	**	**	***	***
	APACHE IV STOP-BANG SOFA			**	*		***	***
	Age, sex, race/ethnicity		*		**	**		
Patient-reported Health Status	PROMIS Global Health					*	***	***
Patient-reported Sleep Quality	PROMIS-SD PROMIS-SRI					*	***	***
Patient-reported Cognitive Function	PROMIS-CF PROMIS-CFA					*	***	***
Cognitive Function	NIH Toolbox Cognition Battery					*	*	*

Note:

* = Data collection in person (measures shaded in grey are temporarily paused)

** = Data collection from the electronic medical record

*** = Data collection via telephone or video conference visit (measures highlighted in yellow are telephone- or video-collected substitutes for in-person visits)

We plan to review approximately 350 medical records in order to achieve our sample size of 182 enrollments during the 4-year study. The data collection schedule is shown in Table 2.

IRB Study Number: 20170771, Version #1.8, Date: 03/10/21, PI: [name]

Table 2. Study Timeline

Activity	Year	Year 1			Year 2			Year 3			Year 4		
	Months	1-4	5-8	9-12	1-4	5-8	9-12	1-4	5-8	9-12	1-4	5-8	9-12
Hire/train personnel													
Database refinement													
Subject recruitment and enrollment													
Subject 1 and 6 month follow up													
Data collection													
Data management													
Analysis of final results													
Final results manuscript													
Final grant report													

8. Study Endpoints

Primary Endpoint. To test the effect of the Family Automated Voice Reorientation (FAVoR) intervention on delirium in critically ill, mechanically ventilated adults during hospitalization in the ICU, we plan for 95% power respectively to detect an effect size (W) of 0.35 using a 2 degrees of freedom Chi-Square Test with a significance level (alpha) of 0.05.

Secondary Endpoint. The recently completed BRAIN-ICU descriptive study of ICU survivors reported a 43% attrition from the inpatient sample to a 12 month follow up time point.¹⁸ Given that a secondary aim of the proposed project plans 1month and 6 months post-hospital discharge follow up, we conservatively planned for a 40% attrition rate, which is a sample size of 182 total (91 in each group).

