the use of actigraphy. In our previously published work⁵⁵⁻⁵⁷ and the preliminary study, we used actigraphy as a surrogate measure of sleep, as have other ICU researchers⁵⁸. Wrist actigraphy also has been found by our research team to be a reliable method of assessing activity and agitation in the ICU.^{55-57,59}

Iatrogenic/Environmental and Biobehavioral Factors. Critical illness and its treatment predispose patients to delirium through several mechanisms which are poorly understood. Factors may include patient characteristics, predisposing conditions, and iatrogenic/environmental factors.

Ambient light. Although the FAVoR intervention does not involve manipulation of ambient light levels, environmental conditions have been hypothesized to influence risk of delirium and may affect sleep in the ICU.

Pharmacological Therapies Affecting Cognition and Sleep. We will collect data regarding specific pharmacologic therapies. For sedatives and narcotics, we will determine equivalent doses to facilitate analysis. To provide sedative and analgesic dose equivalents for analysis, doses will be converted as described in Cammarano et al.⁶⁰

Disease Severity and Comorbid Conditions

Acute Physiology and Chronic Health Evaluation (APACHE) IV. There is strong evidence that severity of illness on admission to the ICU, assessed by APACHE score⁶¹⁻⁶⁵, is a risk factor for delirium.^{4,11}

Sequential Organ Failure Score (SOFA). To determine daily severity of illness we will use the SOFA⁶⁶, which was developed to quantify severity of illness based on the degree of organ dysfunction, serially over time. The SOFA score has good reliability and accuracy,⁶⁷ accurately reflects the daily severity of organ dysfunction, predicts prognosis⁶⁸ and is able to predict ICU mortality.⁶⁹

STOP-Bang Model (SBM) Assessment. Obstructive sleep apnea (OSA) underlies numerous co-morbidities and is linked with cardiovascular and neurovascular diseases, metabolic disorders, and impaired neurocognitive function.⁷⁰⁻⁷² The STOP-Bang Model (SBM) questionnaire will be used as an OSA screening tool for baseline data collection.

Subject Demographics. Subject characteristics that may affect the development of delirium will be collected at admission to the study, including age, race, ethnicity and gender.¹¹

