There will be two parts of the data analysis: Part I: A traditional statistical data analysis for randomized controlled trials for the Primary Specific Aim, and Part II: Pathway analytic model analyses to address the secondary aims. [name] will work closely with the Data Manager to perform all the planned data analyses for this study.

Part I: We will follow the research and regulatory guidelines for statistical analysis of clinical trials including the ICH Guideline⁷⁷ and the CONSORT guidelines⁷⁸. First, descriptive statistics will be performed to describe and compare the characteristics of the intervention and the control groups. Descriptive statistics will be reported as means +/- standard deviation for continuous variables and as frequencies and percentages for categorical variables. Shapes of the data distributions, missing data and outliers will be examined by both graphics and statistical tests. Any data issues identified will be discussed with the PI and other investigators and addressed before formal data analysis. For example, skewed variables may be transformed so that their distributions are close to the Normal Distribution. Outliers may be excluded or included in two separate analyses. Missing data may be imputed or handled by other missing data techniques. Distributions of continuous variables and categorical variables will be compared between the intervention and the control group by using the t-test or Wilcoxon rank sum test and the Chisquare test, respectively. Any baseline covariate that is differentially distributed in the two groups will be adjusted in the subsequent analysis for testing the intervention effect. Assuming the randomization produces well balanced intervention and control groups, a Chi-square test for a 2x2 table with the number of delirium free days and the treatment assignment will be performed to test the primary hypothesis. If there are unbalanced covariates, then covariance adjustment will be performed by using logistic regression that includes both the treatment assignment and the unbalanced covariates. If there are missing values in the primary outcome, then multiple imputation will be performed using SAS PROC MI for missing at random (MAR) data.^{79,80} Sensitivity analysis for potentially not missing at random data will be performed using the Yau and Little⁸¹ Intent-to-Treat Analysis for Longitudinal Studies with Dropouts.

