consent. Step 1 is objective evaluation with the Richmond Agitation-Sedation Scale (RASS) and the Confusion Assessment Method for Intensive Care Unit (CAM-ICU). Patients who score -1, 0, +1 on the RASS indicating drowsy, alert, or restless respectively and are not delirious (CAM-ICU = No) will move to Step 2. Step 2 is assessment for competency using the MacArthur Competence Assessment Tool for Clinical Research: MacCAT-CR that evaluates all four capacity domains for consent (understanding, appreciation, reasoning, expression of a choice). Evaluation of Step 1 requires approximately 2-3 minutes, Step 2 requires approximately 15 minutes. Fan et al.⁷⁶ found in consent evaluations of 150 ICU patients that 89% were sedated/delirious, and unable to provide consent; our experience in previous research is similar. Therefore, we expect that few potential subjects will move to Step 2 while critically ill and mechanically ventilated. The LAR will be contacted for those who fail Step 1 or Step 2. We will evaluate the potential subject's level of orientation and response to our discussions of the study on a daily basis during the hospital phase, and if the potential subject is able to respond in a manner that is clearly understandable, we will use the potential subject's own consent to continue participation. However, in any instance where the potential subject's ability to comprehend and communicate his/her desires is in question, we will seek consent for continued participation from the LAR and will invite the research subject to provide his/her assent. Verbal consent to continue participation and for post-hospital follow up will be obtained from the subject as soon as their medical condition permits. We will follow UM IRB, JMH, and UMH Policies and Procedures.

Non-English-Speaking Subjects

The consenting process for Spanish patients, family members, and/or LAR's will be the same process only with the addition of an individual UMH or JMH Spanish translator or by use of the UMH translation language line phone service, which is available 24 hours a day, 7 days a week.

Cognitively Impaired Adults

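### RASS appears to be scored on every candidate before randomisation but is not scheduled as study data, and the primary analysis prespecifies no baseline covariate; the cost is some precision, not validity

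*Combined protocol and SAP*

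**What the plan says.** **Consent.** The two-step capacity assessment is described in Sections 5, 15 and 26: "Step 1 is objective evaluation with the Richmond Agitation-Sedation Scale (RASS) and the Confusion Assessment Method for Intensive Care Unit (CAM-ICU". The legally authorized representative is approached for those who fail either step, and Section 20 makes the capacity determination part of enrolment. That every candidate is scored is therefore a fair inference, though not an explicit statement. The plan cites a study of 150 ICU patients in which "89% were sedated/delirious, and unable to provide consent" and calls its own experience similar.

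**Data.** RASS has no row in Table 1 (Section 7) and is absent from Sources of Materials and Key Variables in Section 9. On demographics, Section 9 says: "Subject characteristics that may affect the development of delirium will be collected at admission to the study, including age, race, ethnicity and gender". Table 1 does schedule sedative type and cumulative dose from the 24 hours before study entry, CAM-ICU at study admission, and APACHE IV.

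**Analysis.** In the Data Analysis Plan, Part I (Section 10), if the groups are balanced, "a Chi-square test for a 2x2 table with the number of delirium free days and the treatment assignment will be performed". Otherwise: "Any baseline covariate that is differentially distributed in the two groups will be adjusted in the subsequent analysis for testing the intervention effect", using logistic regression. No covariate is named in advance.

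**Power.** Section 8 sets the target: "we plan for 95% power respectively to detect an effect size (W) of 0.35". The test assumed there is a chi-square on 2 df at alpha 0.05. On sample size, the same section adds: "we conservatively planned for a 40% attrition rate, which is a sample size of 182 total (91 in each group").

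**The concern.** Arousal at entry could bear on whether a recorded message is heard, whether CAM-ICU can be scored and how the ICU stay unfolds. If it predicts delirium, leaving it out of the model keeps its variance in the comparison. The imbalance rule does not solve this. It cannot reach a variable that is not in the database, and for recorded variables it decides adjustment after balance has been seen, which does not secure the precision that planned adjustment gives. Randomisation is by permuted blocks with no stratification described, so nothing in the design balances sedation depth. At stake is some power if the true effect is smaller than planned, and an analyst choice that could be removed in advance.

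**Working it through.** **1. The plan's own figure.** Inputs from Section 8: alpha 0.05, power 95%, W = 0.35, 2 df, 40% attrition, N = 182. Power comes from a noncentral chi-square with lambda = N x W^2.

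- 2 df as written: n = 126.07, so 127; 127/0.60 = 212. This does not give 182.
- 2 df, inflated by multiplication: 127 x 1.40 = 178, close to 182.
- 1 df, as a 2x2 table requires: n = 106.08, so 107; 107/0.60 = 179, close to 182.

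Power at 182 subjects is 99.7% (1 df) or 99.2% (2 df). At 109 subjects (182 x 0.60) it is 95.5% or 91.6%. The mismatch in degrees of freedom is a separate matter.

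**2. Gain from a prognostic covariate (approximation).** Effective N = N/(1 - R^2), and the standard error is multiplied by sqrt(1 - R^2). R^2 between baseline RASS and the outcome is not in the documents, so a range is assumed. Power is for 1 df and N = 182.

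| Assumed R^2 | SE factor | Effective N | Power, W = 0.35 | Power, W = 0.20 |
|---|---|---|---|---|
| 0 | 1.000 | 182 | 99.7% | 77.0% |
| 0.02 | 0.990 | 186 | 99.8% | 77.8% |
| 0.05 | 0.975 | 192 | 99.8% | 79.1% |
| 0.10 | 0.949 | 202 | 99.9% | 81.2% |
| 0.20 | 0.894 | 228 | >99.9% | 85.5% |
| 0.30 | 0.837 | 260 | >99.9% | 89.7% |

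At the planned effect the gain is below 1 point. At W = 0.20 it is 0.8 to 12.7 points. If only 109 subjects contributed, power at W = 0.35 would go from 95.5% to between 95.8% and 99.2%. However, the plan ties the 40% attrition to post-discharge follow-up, not to the ICU outcome.

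**3. Logistic simulation with RASS in four groups.** 4,000 trials per setting, N = 182. Assumed shares are 35/35/20/10% and the treatment odds ratio is 0.42; neither comes from the documents.

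| Assumed control risks by group | Unadjusted | Adjusted |
|---|---|---|
| Unrelated to RASS | 82% | 83% |
| Moderate: 75/62/40/75% | 76% | 79% |
| Strong: 85/65/25/85% | 62% | 72% |

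With odds ratio 1, rejection is about 5% for both analyses.

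The moderate case translates to W as follows. Control risk = 0.35(0.75) + 0.35(0.62) + 0.20(0.40) + 0.10(0.75) = 0.6345. Multiplying each group's odds by 0.42 gives a treated risk of 0.437. With mean risk 0.536, W = (0.1975/2)/sqrt(0.536 x 0.464) = 0.198. The same steps give about 0.21 for the unrelated case and 0.17 for the strong case. The simulated effect is thus roughly half the planned one.

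**4. Second simulation, continuous covariate, N = 182, 1,500 trials per setting.** With 80% versus 60% delirium (W = 0.10/sqrt(0.70 x 0.30) = 0.22), power is about 84-85% unadjusted and 86-89% adjusted, at R^2 of about 0.02 to 0.14. With 80% versus 47.6% (W = 0.162/sqrt(0.638 x 0.362) = 0.34), both analyses exceed 99%.

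**5. Narrow range of sedation.** Placing 89% of subjects in the two sedated groups (suggested by the cited study, whose 89% also counts delirious patients) reduces the gain to about 2 points in the moderate case and 4 to 6 in the strong case.

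**6. Chance imbalance.** The SD of the difference between arms in the share deeply sedated is sqrt(2q(1-q)/91). For q = 0.20, 0.35 and 0.50 this is 0.059, 0.071 and 0.074, so a difference of 10 points or more has probability 9%, 16% and 18%.

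**The case against.** The strongest reply is that the plan already covers sedation. Sedative exposure from before study entry is scheduled and converted to dose equivalents, admission CAM-ICU and APACHE IV are also collected, and any of these would be adjusted for if unbalanced. What matters is what RASS adds beyond them, and the simulation compares RASS with no covariate at all. This stands in large part. Dose is exposure and RASS is the resulting state, so they are not interchangeable, but the gain over a model with the scheduled variables may be smaller than shown. The reply also supports the wider point, since none of those variables is prespecified.

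The second reply is that the larger gains need an effect about half the planned one and a strong association (R^2 about 0.22 for one bedside score). That is correct. The direction of the association is also uncertain, because the deepest group may be unscorable on CAM-ICU.

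Two stronger readings are tempting. A reader might infer that the trial holds a RASS value for everyone and discards it; no section says that the score is kept as study data. A reader might also infer that a chance difference in sedation depth biases the result; such differences are already in the test's error rate, and type I error is about 5% either way.

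Finally, a per-patient logistic model needs a binary outcome, whereas the documents give episodes (Section 4), delirium-free days (Section 9) and a 2x2 table of days (Section 10). The outcome must be settled first.

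**Conclusion.** The gap is real and modest. A pre-randomisation measure that the procedure appears to take on everyone is not scheduled as data, and the primary analysis fixes no prognostic covariate in advance. The primary test remains valid. Less than 1 point of power is lost at W = 0.35 with 182 subjects, and about 1 to 10 points at W of about 0.2, depending on a RASS-delirium association that the documents do not give and that may be near zero. Adjustment lost no power in any setting examined. The case for acting is low cost, some protection if the effect is smaller than planned, and removal of a choice made after seeing balance. RASS belongs alongside the scheduled prognostic variables, not as the only covariate.

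**What to change.** 1. Add the Step 1 RASS to Table 1 under Study Admission and to REDCap. For subjects already enrolled, retrieve it from consent or medical records where available, and use a missing category otherwise.
2. In the Data Analysis Plan, Part I, replace the imbalance-triggered adjustment with a prespecified per-patient model: treatment, RASS group (for example -5/-4, -3/-2, -1 to +1, +2 or more, with a stated rule for collapsing sparse groups), and a short list drawn from pre-study sedative dose, admission CAM-ICU and APACHE IV. Fix the list and coding before any comparison by arm.
3. Report the standardised risk difference with the odds ratio, and keep the unadjusted chi-square as supportive.

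The cost is one data field, some record retrieval and revised SAP wording, with no new assessment of patients. The downsides are a few extra parameters (three for four RASS groups, more with a missing category), possibly missing RASS for early subjects, and a conditional odds ratio that needs the marginal difference beside it.
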